11.3.2 Other Secondary Efficacy Endpoints

The change from baseline to Weeks 4 and 8 in faecal calprotectin levels will be descriptively summarised and analysed using a general linear mixed (analysis of covariance (ANCOVA)) model for repeated measures fitted with treatment and stratification factors and visit as fixed effects along with a treatment-by-visit interaction term. The treatment effect (taken from the treatment-by-visit interaction terms at Week 4 and 8), 95% CI and p-values will be presented (*Table 14.2.2.1*).

The change from screening to Week 8 in TMS and the change from baseline to Week 4 and 8 in PMS will be descriptively summarised (*Tables 14.2.2.2* and 14.2.2.3).

The number and proportion of subjects achieving endoscopic remission at Week 8 and the number and proportion of subjects achieving mucosal healing at Week 8 will be descriptively summarised (*Table 14.2.2.4*). Endoscopic remission is defined as a Mayo endoscopic sub-score of zero and mucosal healing is defined as a Mayo endoscopic sub-score of less than or equal to one.

The number and proportion of subjects achieving a clinical response at Week 8 will be descriptively summarised (*Table 14.2.2.5*). Clinical response is defined as the reduction of at least 3 points in TMS and

30% from baseline score with a decrease of at least 1 point in bleeding sub-score or an absolute bleeding sub-score of 0 or 1.

The scores and changes from baseline in the MH and PH component summary measures of the SF-36 questionnaire at Week 4 and Week 8 will be descriptively summarised (*Table 14.2.2.6*).

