9. DATA ANALYSIS AND STATISTICAL CONSIDERATIONS

A summary of the principal features of the statistical analysis of the data will be described here, in the statistical section of the protocol. A more technical and detailed elaboration of the principal features stated in the protocol will be given in the first version of the statistical analysis plan (SAP).

Any amendments to the SAP will be clearly documented and signed prior to the final database lock including justifications and details of their potential impact on the interpretation of the study results.

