9.2. Efficacy Analysis

Analysis of efficacy data will be carried out in the Full Analysis Set in which subjects who prematurely terminate the study will be considered failures.

The primary efficacy endpoint of the study, the rate of subjects responding to treatment. This response rate will be compared in subjects who received ABX464 or placebo by stratified likelihood ratio chi-square test on a 10% one-sided level.

In addition, descriptive statistics will be presented by treatment arm for all secondary efficacy variables for each measurement timepoints separately for the two study groups.

These statistics include:

- Continuous variables: mean, standard deviation, minimum and maximum, stratified 95% confidence intervals, median and quartiles will be presented.
- Categorical variables: counts, rates and stratified 95% confidence intervals for the rates will be calculated.

In addition to descriptive statistics, the following analyses will also be carried out for the variables indicated below:

- Kaplan-Meier estimates and plots will be presented for time to UC worsening after week 8.
- Mixed model analysis of covariance will be conducted for the following measurements:
 - O The change from screening in IL-22 expression levels in serum and rectal/sigmoidal tissue at week 8,
 - O The change from baseline in microRNA-124 levels in whole blood (PAXgene®) and in tissue (RNA later) at week 4 and week 8,
 - O The change from baseline in fecal calprotectin levels at week 4 and week 8,
 - O The change from screening in the histopathology/infiltrate (rectal/sigmoidal biopsies) assessed by the Geboes score at week 8,

In this model, treatments and stratum will be fixed effects, subjects will be random effect and baseline values of the respective measurements will be covariates. Other explanatory variables will also be allowed to be included in the model. In order to normalize eventual skewed distributions transformation of the data will also be considered. Study groups will be compared within this model framework. All p-values will be interpreted in a descriptive manner.

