1 INTRODUCTION

1.1 GENERAL

This statistical analysis plan (SAP) describes the statistical methods to be used during the reporting and analyses of data collected under Abivax Protocol ABX-464-001 and should be read in conjunction with the study protocol and electronic case report form (eCRF).

This version of the plan has been developed using the protocol Version 2.0 dated 13MAR2018 annotated eCRF Version 3.0 dated 11APR2018. Any further changes to the protocol or eCRF will be reviewed for potential impact on the SAP which will be amended if it is deemed necessary.

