11.2.3 Disease History and Characteristics

Time since UC diagnosis (years) will be summarised for the FAS (*Table 14.1.6*) and is derived as (date of informed consent - date of UC diagnosis) / 365.25. The stratification factors, concomitant treatment with corticosteroids (yes, no) and previous biologics exposure (yes, no), will be summarised within the same table.

The faecal calprotectin levels recorded at baseline will be summarised descriptively (*Table 14.1.7*). TMS, PMS and MH and PH component summary measures from the SF-36 questionnaire collected at baseline will be also be summarised descriptively within the same table. Note that the TMS encompasses the PMS (number of stools, blood in stools and severity assessment) and the endoscopy sub-score. The baseline endoscopy is performed at screening while the PMS is assessed both during the screening and the Day

0 visits. Therefore the baseline TMS value will be derived by adding the endoscopy sub-score performed at screening with the PMS done at Day 0.

The number and proportion of patients with concomitant use of medications for UC will be summarised by all categories, some of which are corticosteroid only, immunosuppressants only, combination treatment or no treatment (*Table 14.1.8*). The number and proportion of patients with prior biological failure (categorised as TNF or others / vedolizumab) will also be presented within the same table.

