		(N=xx)	(N=xx)	(N=xx)
Concomitant Use of Medications for UC	N	xx	××	xx
	Corticosteroid only	xx (xx.x%)	xx (xx.x%)	XX (XX.X%)
	Immunosuppressants only	xx (xx.x%)	xx (xx.x%)	xx (xx.x%)
	Combination treatment	xx (xx.x%)	xx (xx.x%)	xx (xx.x%)
	No treatment	xx (xx.x%)	xx (xx.x%)	xx (xx.x%)
	Eto			
Prior biological failure	N	xx	xx	xx
	TNF or others	xx (xx.x%)	xx (xx.x%)	xx (xx.x%)
	Vedolizumab	xx (xx.x%)	xx (xx.x%)	xx (xx.x%)

The denominator for each percentage is the number of non-missing observations within the column

Source: Listing 16.x.x

Path\Filename Page x/y

Programming note : include all possible categories for 'Concomitant Use of Medications for UC', the above list is not complete.

Version date: 23 August 2018

Page 37 of 93

SIMBEC ORION GROUP

		ABX-464 (N≍xx)	Placebo	p-value
	··········		(N=xx)	xx)
Clinical Remission at Week 8	N	xx	xx	
	Yes	xx (xx.x%)	xx (xx.x%)	
	No	xx (xx.x%)	xx (xx.x%)	

Remission excludes friability and is based on the Total Mayo Score being less than or equal to two, with no individual subscore greater than one.

Response rate between treatments is compared using stratified likelihood ratio chi-square test at a one-sided 10% significance level.

Source: Listing 16.x.x

Path\Filename

Page x/y

This layout also applies to:
Table 14.2.1.2 Analysis of Patients Achieving Clinical Remission (full Analysis Set)

Version date: 23 August 2018

Page 38 of 93

Table 14.2.2.1 Analysis of Faecal Calprotectin Levels (Per Protocol Set)

ddMMMyyyy

	ABX-464 Placebo	Placebo	Treatment effect (95% CI): ABX-464 vs Placebo	p-value	
		(N=xx)	(N=xx)	WDX.404 A2 LINCERO	
Baseline	N	××	xx		
	Mean	xx.xx	xx.xx		
	SD	xx.xx	xx.xx		
	Median	xx.xx	xx.xx		
	Minimum	xx.x	xx.x		
	Maximum	xx.x	xx.x		
Week 4	N	xx	××		
	Mean	xx.xx	xx.xx		
	Etc				
Change from baseline to Week 4	N	xx	xx		
	Mean	xx.xx	xx.xx		
	Etc				
Week 8	N	xx	xx		
	Mean	xx.xx	xx.xx		
	Etc				
Change from baseline to Week 8	N	xx	xx		

Version date: 23 August 2018

Page 39 of 93

SIMBEC ORION GROUP

	Mean Etc	xx.xx	xx.xx		
Repeated measures	Treatment at Week 4			xx.x (xx.x, xx.x)	x.xxx
	Treatment at Week 8			xx.x (xx.x, xx.x)	x.xxx
	Concomitant use of corticosteroids				x.xxxx
	Previous biologics				x.xxx
	exposure Visit				x.xxxx

ANCOVA model is fitted with treatment, stratification factors and visit as fixed.

Source: Listing 16.x.x Path\Filename

Page x/y

Version date: 23 August 2018

Page 40 of 93

ddMMMyyyy

ABX464-101

Table 14.2.2.2 Summary of Total Mayo Score (Per Protocol Set)

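### SAP 11.3.2 and the Table 14.2.2.1 shell leave out the baseline faecal calprotectin covariate that Protocol 9.2 specifies, at a likely cost in precision

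*SAP*

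**What the plan says.** Protocol 9.2 lists the measurements that go into a mixed-model analysis of covariance. One of them is "The change from baseline in fecal calprotectin levels at week 4 and week 8". Treatment and stratum are fixed effects in that model, and "subjects will be random effect and baseline values of the respective measurements will be covariates". The protocol also lets other explanatory variables be added and allows transformation of skewed data. It treats all these p-values as descriptive.

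SAP 11.3.2 takes up the same endpoint, calls the model a general linear mixed (ANCOVA) model, and specifies it as a "model for repeated measures fitted with treatment and stratification factors and visit as fixed effects along with a treatment-by-visit interaction term". Estimates, 95% CIs and p-values are reported for Weeks 4 and 8. The shell for Table 14.2.2.1 (SAP 15) has model rows for treatment at each week, "Concomitant use of corticosteroids", previous biologics exposure and visit. Its footnote reads "ANCOVA model is fitted with treatment, stratification factors and visit as fixed". SAP 14.1 assigns the table to the PP set only.

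On how the two documents relate, SAP 1.1 says that the SAP "should be read in conjunction with the study protocol". Protocol 9 describes the SAP as "A more technical and detailed elaboration of the principal features stated in the protocol".

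**The concern.** Two governing documents specify different models for one endpoint, and the later, more operational one drops a named term without comment. Taking change from baseline does not replace the covariate. Subtraction fixes the slope of follow-up on baseline at 1, whereas the covariate lets the data estimate it. When the true slope is below 1, as is usual with regression to the mean, the change-score model leaves avoidable variance in the treatment effect.

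What is at stake is the width of the Week 4 and Week 8 intervals for the only secondary efficacy endpoint that this SAP fits with a regression model. With at most about 20 versus 10 subjects, those intervals are its main inferential output. Carry-over of chance baseline imbalance is part of the same precision loss, not a further cost.

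**Working it through.** **Step 1. Terms side by side.**

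| Term | Protocol 9.2 | SAP 11.3.2 | Table rows | Table footnote |
|---|---|---|---|---|
| Treatment | yes | yes | by week | yes |
| Stratification factors | yes | yes | yes | yes |
| Visit | not named | yes | yes | yes |
| Treatment-by-visit | not named | yes | implied by weekly rows | no |
| Subject as random effect | yes | not named | no row | no |
| Baseline calprotectin | yes | no | no | no |

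The footnote is incomplete in its own right, since it omits treatment-by-visit, so it proves little alone. The SAP text and the rows agree with it on baseline.

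**Step 2. Inputs.** From the documents: 30 subjects at 2:1, so 20 and 10 (Protocol 9.4, SAP 3.5); two binary strata (SAP 3.6); 95% CI (SAP 11.3.2). Not in the documents, so assumed: the baseline/follow-up correlation ρ, the ratio k = follow-up SD / baseline SD, and normal data. The plan gives no precision figure for calprotectin to reproduce. Its 81% power concerns the remission comparison (recomputed: 81.9%) and does not use this model.

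**Step 3. Formula, one follow-up visit.** The residual variance of change without baseline is s0² + s1² − 2ρ·s0·s1. With baseline it is s1²(1 − ρ²). The ratio is

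V = (1 + k² − 2ρk) / [k²(1 − ρ²)], which is 2/(1 + ρ) when k = 1.

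Residual df are 30 − 4 = 26 without baseline and 25 with it. Estimating the slope multiplies the adjusted variance by 1 + 1/(26 − 2) = 1.0417. The t quantiles are 2.0555 and 2.0595. So

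width ratio (without / with) ≈ √(V/1.0417) × 2.0555/2.0595.

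**Step 4. Equal SDs (k = 1).** At ρ = 0.5, V = 2/1.5 = 1.333, and √(1.333/1.0417) × 0.998 = 1.13. Likewise:

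| ρ | V | Formula | Simulation (20,000 trials) |
|---|---|---|---|
| 0.3 | 1.538 | 1.21 | 1.213 |
| 0.5 | 1.333 | 1.13 | 1.130 |
| 0.7 | 1.176 | 1.06 | 1.062 |
| 0.9 | 1.053 | 1.00 | 1.003 |
| 0.95 | 1.026 | 0.99 | 0.991 |

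Break-even is where V = 1.0417 × (2.0595/2.0555)² = 1.046, so ρ = 2/1.046 − 1 ≈ 0.91. It falls to about 0.88 to 0.89 with 24 subjects.

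Simulating two visits with a subject random effect (20:10, Week 8 contrast, Week 4/Week 8 correlation 0.6) gives 1.227, 1.141 and 1.074 at ρ = 0.3, 0.5 and 0.7.

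**Step 5. Unequal SDs, 30 subjects, same formula.**

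| k | ρ 0.3 | 0.5 | 0.7 | 0.8 | 0.9 |
|---|---|---|---|---|---|
| 0.8 | 1.38 | 1.29 | 1.23 | 1.22 | 1.25 |
| 0.9 | 1.28 | 1.20 | 1.13 | 1.10 | 1.09 |
| 1.25 | 1.10 | 1.03 | 0.99 | 0.98 | 1.00 |
| 1.5 | 1.05 | 1.00 | 0.98 | 1.00 | 1.11 |

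The downside of adjusting is bounded. The numerator of V exceeds its denominator by (1 − kρ)², so V is never below 1, and the smallest possible ratio is √(1/1.0417) × 0.998 = 0.978. For k below 1, V is smallest at ρ = k, where it equals 1/k². At k = 0.9 that is 1.235, a width ratio of 1.09. Hence the unadjusted interval is wider at every ρ when k is 0.9 or less.

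**The case against.** The strongest reply is that nothing has changed. The SAP calls the model mixed and ANCOVA, is to be read with the protocol, and lists its terms as fixed effects, whereas the protocol names fixed effects, random effect and covariates separately. The SAP omits the random subject effect too, the footnote is visibly shorthand, and SAP 15 lets the programmer alter layouts. So a reader who infers that the sponsor deliberately abandoned the protocol model goes further than the documents do. What remains is that no covariate is named anywhere in the SAP's specification. The protocol's flexibility is to add variables, not remove baseline, and SAP 10.1 allows other methods only if assumptions fail in the final data.

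Three other stronger readings also fail:

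- **A flat 0.9 rule.** A reader might infer that omission costs precision at any correlation below about 0.9 and at none above it. That needs equal SDs, which no document states. At k = 1.25 the unadjusted interval is slightly narrower at 0.7 and 0.8. At k = 0.8 it is about 25% wider at 0.9.
- **Bias caused by the omission.** Randomisation alone would make both estimates unbiased. The table uses the PP set, which requires completion to D56 and no major deviation (SAP 6.3). That is selection after randomisation, so unbiasedness is not guaranteed with or without baseline.
- **Damage to error rates or power.** Protocol 9.2 makes these p-values descriptive, and no sample-size figure rests on this model.

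It is also fair to say that the widening is an average. In simulated single-visit trials at 20:10 with equal SDs, the interval without baseline was the narrower one in 4%, 11% and 26% of runs at ρ = 0.3, 0.5 and 0.7, and in 57% at 0.9.

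**Conclusion.** The mismatch is established from the text: Protocol 9.2 requires the baseline covariate for this endpoint, and SAP 11.3.2 and the shell do not include it or explain its absence. Whether it was meant cannot be told.

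The numerical cost depends on quantities the plan does not give. At moderate correlations and equal SDs it is roughly 6% to 21% of interval width. It is larger if calprotectin is less variable at follow-up than at baseline. If it is more variable, omission can bring a small gain, at most about 2% with 30 subjects. That ceiling is about 3% with 24 subjects: √(1/1.0556) × 2.0860/2.0930 = 0.970, where 1.0556 = 1 + 1/18. The balance favours including baseline. The consequence is confined to the precision of one secondary endpoint, so this is a correction worth making and not a threat to the trial's conclusions.

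**What to change.** Add Day 0 faecal calprotectin as a covariate in SAP 11.3.2, on the same scale as the analysed response (transformed if the response is transformed). Add a matching row to Table 14.2.2.1 and name the term in its footnote. If leaving it out was intended, state and justify the departure from Protocol 9.2 in the SAP before unblinding. Protocol 9 already requires SAP amendments to be justified and signed before final database lock, and SAP 9.3 loads the randomisation list only after lock.

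The cost is one model term, one degree of freedom and a shell edit. No new data are needed. The Day 0 sample is in the protocol flow chart, and SAP 11.2.3 already states: "The faecal calprotectin levels recorded at baseline will be summarised descriptively".

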2.4. Secondary Endpoints

The secondary endpoints of this study are:

Primary efficacy endpoint:

The proportion of subjects receiving ABX464 with clinical remission according to the Total Mayo Score
at week 8 compared to placebo. Remission exclude friability and is based on total Mayo score ≤ 2 with
no individual sub-score > 1.

Other secondary endpoints:

- The change from screening in IL-22 expression levels in serum and rectal/sigmoidal tissue at week 8 compared to placebo.
- The change from baseline in microRNA-124 levels in whole blood (PAXgene®) and in tissue (RNA later) at week 4 and week 8 compared to placebo.
- The change from baseline in fecal calprotectin levels at week 4 and week 8 compared to placebo.
- The change from screening in the histopathology/infiltrate (rectal/sigmoidal biopsies) assessed by the

Geboes score at week 8 compared to placebo.

- The change from screening in rectal microbiota using taxonomic markers at week 8 compared to placebo.
- The change from screening in Total Mayo Score in subjects receiving ABX464 at week 8 compared to placebo.
- The change from baseline in Partial Mayo Score in subjects receiving ABX464 at week 4 and week 8 compared to placebo.
- The proportion of subjects achieving endoscopic remission at week 8. Endoscopic remission is defined as a Mayo endoscopic sub-score of 0.
- The proportion of subjects achieving improvement in endoscopic appearance at week 8. Improvement of endoscopic appearance is defined as a Mayo endoscopic sub-score of ≤ 1.
- The proportion of subjects achieving a symptomatic remission at week 8. Symptomatic remission is
 defined as a total Mayo Score ≤ 2 with no individual sub-score > 1 and rectal bleeding and stool
 frequency sub-scores of 0.
- The time to UC worsening after week 8.
- The serum concentration evaluation of ABX464 and its metabolites levels.
- The scores and changes from baseline in SF-36 Questionnaire scores at week 4 and week 8.
- The number of incidences of treatment-emergent serious adverse events.
- The number of incidences of treatment-emergent adverse events of special interest.
- The number of incidences of adverse events leading to investigational product discontinuation.
- The number of incidences of specific laboratory abnormalities.

[figure not shown]

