5. STUDY ASSESSMENTS AND PROCEDURES

5.1. Study Flow Chart

A detailed study flow chart (with all assessments) is displayed hereafter.

			Study Treatment Period								
	D-14	Randomization	D0	D7	D14	D21	D28	D42	D56	D63- EOS	
Time Window	±3 days			±2 days	±2 days	±2 days	±2 days	±4 days	±4 days	±2 days	
Obtained Inform Consent	X										
Check of IN/EX Criteria	Х	X									
Physical Examination	X		Х	X	X	X	X	X	Χ	X	
Body Weight (kg)	Х		X	X	X	X	Х	Х	X	X	
Height Measurement (cm)	X										
Medical History and Concomitant Medications	Х			-							
Vital signs	X		X	X	X	X	X	X	X	X	
ECG (12 lead)	X		X				X		X	Х	
Randomization		X		1							
Blood Pregnancy test (wocse)	X		X	1			X		X		
Hematology + Blochemistry	Х		X	X	Х		Χ		X	Х	
Mayo score (Total or Partial)	X		X	X	X	Х	X	X	X.	X	
Faecal calprotectin			X				X		Х	X	
Rectal microbiota	X						 	1	X		
Sigmoldoscopy	X		 					1	Х		
SF-38 (Questionnaire)			Х			ļ	X]	X		
ABX464/placebo treatment dispensation and subject diary review			×				X				
Blood samples drug pK			X,				Χ·				
Samples for miRNA (Paxgene tubes)			Х				х		X		
Adverse Events recording		I	X	X	l X	X	Х	X	X	 	

^{*} Applicable to the first 9 subjects randomized / PK predose, 0.5, 1, 1.5, 2, 2.5, 3, 4, 8 and 12 post-dose

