4.2.2 Other Secondary Endpoints

- The change from baseline in faecal calprotectin levels at Week 4 and Week 8 compared to placebo.
- The change from screening in TMS in subjects receiving ABX464 at Week 8 compared to placebo.
- The change from baseline in Partial Mayo Score (PMS) in subjects receiving ABX464 at Week 4 and Week 8 compared to placebo.
- The proportion of subjects achieving endoscopic remission at Week 8. Endoscopic remission is defined as a Mayo endoscopic sub-score of zero.
- The proportion of subjects achieving mucosal healing at Week 8. Mucosal healing is defined as a Mayo endoscopic sub-score of less than or equal to one.
- The proportion of subjects achieving a clinical response at Week 8. Clinical response is defined
 as the reduction of at least 3 points in TMS and 30% from baseline score with a decrease of at
 least 1 point in bleeding sub-score or an absolute bleeding sub-score of 0 or 1
- The scores and changes from baseline in mental health (MH) and physical health (PH) component summary measures of the SF-36 Questionnaire at Week 4 and Week 8.
- The number of incidences of TEAEs.
- The number of incidences of TEAEs of special interest.
- The number of incidences of TEAEs leading to investigational medicinal product (IMP) discontinuation.

• The number of incidences of specific laboratory abnormalities.

The following list includes all endpoints to be assessed by Abivax. The methods for their analysis are not included in this SAP:

- The change from screening in IL-22 expression levels in serum and rectal/sigmoidal tissue at Week 8 compared to placebo.
- The change from baseline in microRNA-124 levels in whole blood (PAXgene®) and in tissue (RNA later) at Week 4 and Week 8 compared to placebo.
- The change from screening in the histopathology/infiltrate (rectal/sigmoidal biopsies) assessed by the Geboes score at Week 8 compared to placebo.
- The change from screening in rectal microbiota using taxonomic markers at Week 8 compared to placebo.

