		ABX-464	Placebo	
		(N=xx)	(N=xx)	
Baseline	N	xx	××	
	Mean	xx.xx	xx.xx	
	SD	xx.xx	xx.xx	
	Median	xx.xx	xx.xx	
	Minimum	xx.x	xx.x	
	Maximum	xx.x	xx.x	
Veek 8	N	xx	xx	
	Mean	xx.xx	xx.xx	
	SD	xx.xx	xx.xx	
	Median	xx.xx	xx.xx	
	Minimum	xx.x	xx.x	
	Maximum	xx.x	xx.x	
Change from baseline to Week 8	N	xx	xx	
· ·	Mean	xx.xx	xx.xx	
	SD	xx.xx	xx.xx	
	Median	xx.xx	xx.xx	
	Minimum	xx.x	xx.x	
	Maximum	xx.x	xx.x	

Version date: 23 August 2018

Page 41 of 93

Source: Listing 16.x.x Path\Filename

Page x/y

Version date: 23 August 2018

Page 42 of 93

Table 14.2.2.3 Summary of Partial Mayo Score (Per Protocol Set)

ddMMMyyyy

		ABX-464	Placebo
		(N=xx)	(N=xx)
Baseline	И	xx	xx
200023111	Mean	xx.xx	xx.xx
	SD	xx.xx	xx.xx
	Median	xx.xx	xx.xx
	Minimum	xx.x	xx.x
	Maximum	xx.x	xx.x
Week 4	N	xx	xx
	Mean	xx.xx	xx.xx
	Etc		
Change from baseline to Week 4	N	xx	xx
	Mean	xx.xx	xx.xx
	Eto		
Week 8	N	xx	xx
	Mean	xx.xx	xx.xx
	Etc		
Change from baseline to Week 8	N	xx	xx
	Mean	xx.xx	xx.xx
	Etc		

Version date: 23 August 2018

Page 43 of 93

Source: Listing 16.x.x Path\Filename

Page x/y

Version date: 23 August 2018

Page 44 of 93

ABX464-101 ddMMMyyyy Table 14,2,2,4 Summary of Patients Achieving Endoscopic Remission and Mucosal Healing (Per Protocol Set)

		ABX - 464	Placebo
		(N=xx)	(N=xx)
Endoscopic remission at Week 8	N	xx	xx
	Yes	xx (xx.x%)	xx (xx.x%)
	No	xx (xx.x%)	xx (xx.x%)
Mucosal healing at Week 8	N	xx	xx
	Yes	xx (xx.x%)	xx (xx.x%)
	No	xx (xx.x%)	xx (xx.x%)

Endoscopic remission is defined as a Mayo endoscopic sub-score of zero. Mucosal healing is defined as a Mayo endoscopic sub-score of less than or equal to one.

Source: Listing 16.x.x Path\Filename

Page x/y

Version date: 23 August 2018

Page 45 of 93

ddMMMyyyy

ABX464-101

Table 14.2.2.5 Summary of Patients Achieving Clinical Response (Per Protocol Set)

		ABX-464	Placebo
		(N=xx)	(N=xx)
Clinical response at Week 8	N	xx	xx
	Yes	xx (xx.x%)	xx (xx.x%)
	No	xx (xx.x%)	xx (xx.x%)

Clinical response is defined as the reduction of at least 3 points in TMS and 30% from baseline score with a decrease of at least 1 point in bleeding sub-score or an absolute bleeding sub-score of 0 or 1

Source: Listing 16.x.x

Path\Filename

Page x/y

Version date: 23 August 2018

Page 46 of 93

ABX464-101 ddMMMyyyy
Table 14.2.2.6 Summary of SF-36 Component Summary Measures Scores (Per Protocol Set)

		ABX-464	Placebo
		(N≖xx)	(N=xx)
ental Health Component Summary Measure			
Baseline	N	xx	××
	Mean	xx.xx	xx.xx
	SD	xx.xx	xx.xx
	Median	xx.xx	xx.xx

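### Change in Total and Partial Mayo Score is defined against placebo, but the SAP tabulates each arm alone, with no between-arm difference or confidence interval

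*SAP*

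**What the plan says.** The endpoints are comparative in both documents. Protocol 2.4 lists "The change from screening in Total Mayo Score in subjects receiving ABX464 at week 8 compared to placebo" and "The change from baseline in Partial Mayo Score in subjects receiving ABX464 at week 4 and week 8 compared to placebo". SAP 4.2.2 repeats the first as "The change from screening in TMS in subjects receiving ABX464 at Week 8 compared to placebo" and words the Partial Mayo endpoint in the same comparative way.

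The planned analysis, in SAP 11.3.2, is one sentence: "The change from screening to Week 8 in TMS and the change from baseline to Week 4 and 8 in PMS will be descriptively summarised". Shell 14.2.2.2 gives N, mean, SD, median, minimum and maximum by arm for Total Mayo at baseline, Week 8 and change. Shell 14.2.2.3 does the same for Partial Mayo at baseline, Week 4, Week 8 and the two changes. Both tables use the per-protocol set.

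Faecal calprotectin, in the same SAP section, gets a repeated-measures model. For it, "The treatment effect (taken from the treatment-by-visit interaction terms at Week 4 and 8), 95% CI and p-values will be presented".

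Protocol 9.2 requires descriptive statistics for all secondary efficacy variables "for each measurement timepoints separately for the two study groups", and for continuous variables it lists stratified 95% CIs and quartiles. Its mixed-model list covers IL-22, miR-124, calprotectin and the Geboes score. Neither Mayo score is on that list.

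**The concern.** An endpoint defined against placebo needs an output that states the contrast with placebo, and none is planned for these two. After remission, the Mayo scores are the most direct clinical evidence of efficacy in the trial, yet a stool biomarker gets an estimated treatment effect and they do not. The reader of the report would compare two unadjusted means by eye, from at most 20 and 10 subjects, with no printed measure of how uncertain their difference is. Randomisation is stratified on two factors, and neither enters these summaries.

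Separately, the SAP gives less than the protocol's own descriptive rule on both intervals and timepoints.

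**Working it through.** **1. The plan's own figures.** Neither document gives an SD, target difference or power for Mayo change. The only related figure is 81% power for the primary efficacy endpoint (0.6 vs 0.2, 20 vs 10, one-sided 10%). Pooled rate = (12 + 2)/30 = 0.467. Null SE = √(0.467 × 0.533 × 0.15) = 0.193. Alternative SE = √(0.6×0.4/20 + 0.2×0.8/10) = 0.167. Power = Φ((0.4 − 1.2816 × 0.193)/0.167) = 81.9%, which agrees with the stated 81%. This confirms the sample size and allocation used below. It says nothing about the Mayo scores.

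**2. Endpoint against output.**

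| Variable | Endpoint wording | SAP 11.3.2 | Shell |
|---|---|---|---|
| Total Mayo, Week 8 | against placebo | descriptive | 14.2.2.2: arm columns only |
| Partial Mayo, Weeks 4 and 8 | against placebo | descriptive | 14.2.2.3: arm columns only |
| Calprotectin, Weeks 4 and 8 | against placebo | repeated-measures model | 14.2.2.1: effect, 95% CI, p-value |

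Planned between-arm estimates for the two Mayo changes: none.

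**3. Do general clauses fill the gap?** SAP 11.3 says that treatment comparisons set ABX464 against placebo, but gives no method for these variables. SAP 10.1 allows CIs and quartiles in statistical analysis outputs where appropriate, and leaves the format of summaries to the shells. The shells for these two tables, titled as summaries rather than analyses, show neither.

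**4. Timepoints.** Protocol 5.1, 5.2.4, 5.2.5 and 5.3.5 place a Mayo assessment at every visit. The on-treatment, post-baseline visits are D7, D14, D21, D28, D42 and D56, six in all. D56 counts because the Total Mayo contains the Partial Mayo items (SAP 11.2.3). Shell 14.2.2.3 uses D28 and D56, so 6 − 2 = 4 visits are not summarised. Their scores appear only in Listing 16.4.5.1.

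**5. Which baseline for Total Mayo.** SAP 4.2.2 and 11.3.2 take change from screening. Shell 14.2.2.2 shows change from baseline. SAP 11.2.3 builds baseline Total Mayo from the screening endoscopy sub-score plus the Day 0 Partial Mayo. The two starting values share the endoscopy item and can differ in the other three.

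**6. Precision of the missing difference.** The SDs and the correlation are assumptions; 20 and 10 subjects come from the plan.

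- SE = SD × √(1/20 + 1/10) = SD × 0.387.
- Unadjusted half-width = t(0.975, 28 df) × SE = 2.048 × SE.
- Adjusted half-width = t(0.975, 25 df) × SE × √(1 − r²), with r = 0.5 between baseline and change: 2.060 × 0.866 × SE = 1.784 × SE. The 25 df are 30 minus intercept, treatment, two stratification factors and baseline.

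| Assumed SD of change | SE | Unadjusted | Adjusted, r = 0.5 |
|---|---|---|---|
| 1.5 | 0.581 | 1.19 | 1.04 |
| 2.0 | 0.775 | 1.59 | 1.38 |
| 2.5 | 0.968 | 1.98 | 1.73 |
| 3.0 | 1.162 | 2.38 | 2.07 |
| 3.5 | 1.356 | 2.78 | 2.42 |

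The main range is 2.5 to 3.5. The smaller SDs are shown because Partial Mayo runs to 9 points and Total Mayo to 12. All rows assume that all 30 subjects contribute. The per-protocol set may be smaller, which would widen the intervals.

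**The case against.** The best defence is that descriptive reporting was chosen and is consistent. Protocol 9.2 leaves both Mayo scores off its model list, the SAP follows, safety is the primary objective, the trial is a 30-subject Phase IIa study, and p-values on secondary variables are descriptive in any case. Side-by-side arm summaries can be read as a comparison of a kind. This stands to the extent that no formal test is required. It does not explain why the contrast goes unestimated, nor why the SAP drops the intervals and timepoints that protocol 9.2 requests even for descriptive reporting.

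A reader might infer that the report could not say how much better ABX464 did. That goes too far: the unadjusted difference and its CI can be worked out from each arm's N, mean and SD. What is missing is the printed contrast and the adjustment.

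A reader might also infer that the four unsummarised visits cause the missing treatment effect. They do not. The Partial Mayo endpoint is defined at Weeks 4 and 8 only, and the effect is missing because the analysis is descriptive. Nor would modelling those visits be equivalent to recruiting more subjects. Such a gain belongs to an average over visits, which is not the endpoint, and it depends on correlations that the documents do not give.

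The same argument does not extend to SF-36, whose endpoint is not worded against placebo in either document.

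**Conclusion.** The point holds as a mismatch between endpoint and analysis. Two comparative secondary endpoints receive no planned between-arm estimate, and their summaries fall short of protocol 9.2 on CIs and timepoints. These are two separate gaps: the protocol's descriptive rule concerns statistics by arm, and meeting it would not by itself supply the contrast.

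The size depends on an assumed SD. At 2.5 to 3.5 points, the unprinted uncertainty is about ±2.0 to ±2.8 points unadjusted and ±1.7 to ±2.4 adjusted at a baseline correlation of 0.5; smaller SDs give proportionately narrower intervals. This is a loss of information on secondary endpoints that can be recovered at almost no cost. It does not affect the primary efficacy or safety results.

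**What to change.** Amend the SAP before database lock, with the justification that protocol section 9 requires for SAP amendments.

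1. **Total Mayo baseline.** Choose the starting value, and make SAP 4.2.2, 11.2.3, 11.3.2 and shell 14.2.2.2 agree. Do this first, because the covariate depends on it.
2. **Table 14.2.2.2.** Add the Week 8 difference (ABX464 minus placebo) with 95% CI, from an ANCOVA on treatment, the two stratification factors and the baseline value.
3. **Table 14.2.2.3.** Add the Week 4 and Week 8 differences with 95% CIs, from the same kind of repeated-measures model as calprotectin, with the Day 0 value as covariate. Write that covariate out, since the calprotectin description in SAP 11.3.2 does not name one. State the covariance structure; with two visits, an unstructured matrix has three parameters (two variances and one covariance).
4. **Descriptive part.** Summarise Partial Mayo at D7, D14, D21, D28, D42 and D56. For both scores, give the stratified 95% CIs and quartiles from protocol 9.2, or state and justify leaving them out.
5. **P-values.** Label any as descriptive.

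The cost is SAP wording, some programming and extra rows in two existing tables. No new data or visits are needed.
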